## 7.5.2 **Duration of Objective Response**

Duration of objective response is defined as the time from the first documentation of objective response by the investigator that is subsequently confirmed at a visit that is  $\geq 28$  days later to disease progression or death due to any cause.

Duration of response (months) = (earliest date of progressive disease or death due to any cause or censoring – date of first objective response + 1)/30.4375

Duration of objective response will be computed only among subjects who experience an objective response (confirmed CR or confirmed PR). Dates of progression and censoring will be determined as described for the secondary endpoint analysis of PFS (see section 7.2.1).

Duration of objective response will be analyzed using the same analysis method (Kaplan-Meier) as for the analysis on PFS (see Section 7.2.1.3).

The analyses for duration of response will be performed only if ORR >10%.

# 7.5.3 Time to Objective Response

Time to objective response is defined as the time from randomization to the first documentation of objective response by the investigator that is subsequently confirmed at a visit that is  $\geq 28$  days later to disease progression or death due to any cause.

Time to objective response (months) = (date of first objective response - date of randomization + 1)/30.4375

Time to objective response will be computed only among subjects who experience an objective response (confirmed CR or confirmed PR), and arithmetic methods (not Kaplan-Meier) will be used.

The analyses for time to response will be performed only if ORR >10%.

# 7.5.4 Alpha-fetoprotein (AFP)

For each scheduled post-baseline visit the AFP values at baseline and change from baseline will be summarized with standard descriptive statistics by treatment arm. Descriptive statistics for best/worst percent change since baseline will also be presented per arm using all available data. Waterfall plot will be presented by treatment arm for best percent change since baseline.

Best change is defined as the largest reduction (or smallest increase if no reduction) and worst change is defined as the largest increase (or smallest reduction if no increase). Appropriate transformations may be applied to normalize the data for presentation or analysis.

## 7.5.5 Serum Bone Markers

Serum bone markers (CTx, and BSAP) results at baseline, Week 3, Week 5 and Week 9 will be summarized by descriptive statistics. In addition, percent change from baseline at Week 3, Week 5 and Week 9, as well as best/worst percent change from baseline will be presented per arm using all available data.

Best change is defined as the largest reduction (or smallest increase if no reduction) and worst change is defined as the largest increase (or smallest reduction if no increase). These summaries will be provided for all subjects in the ITT population.

Appropriate transformations may be applied to normalize the data for presentation or analysis.

The best percent change from baseline for CTx and BSAP will be displayed graphically for each arm using waterfall plots. However, for CTx, subjects with baseline values that are below the limit of quantification (BLQ) will not be included in summaries or figures.

# 7.5.6 Child-Pugh Scores

Change from baseline in Child-Pugh categories will be summarized as a shift table at each time point through to end of treatment.

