Clinic visits for safety evaluations will occur prior to dosing on W1D1 and at minimum every 2 weeks ( $\pm$  3 days) after treatment is initiated through W9D1 and then every 4 weeks ( $\pm$  5 days) thereafter independent of any dose interruptions. The final safety assessment will occur at the post-treatment follow-up visit 30 (+14 days after the date of the decision to discontinue treatment) unless a Grade 3/4 AE or an SAE is determined to be ongoing (see Section 8.3.4).

If study treatment is interrupted, investigators should perform additional safety assessments weekly or more frequently as clinically indicated. Results of safety assessments should be reviewed as soon as they become available in order to make timely decisions regarding the continuation, interruption, or restarting of study treatment.

Radiographic tumor assessments (Section 5.7.6) and HRQOL assessments (Section 5.7.8) should be performed according to the schedule in Appendix A (Appendix B for the Open-Label Phase, Appendix C for the Maintenance Phase [HRQOL will not be assessed in the Open-Label Phase or Maintenance Phase]).

In accordance with the ITT principle, HRQOL, and radiographic tumor assessments, as well as survival follow-up, are to be performed per protocol even for subjects randomized but who never receive study treatment. For such subjects, W1D1 is defined as the date of randomization.

Child-Pugh Score every 8 weeks ( $\pm$  5 d) after randomization (W9D1, W17D1 etc). Child-Pugh assessments should continue regardless of whether study treatment is given, reduced, interrupted, or discontinued until the later of 8 weeks after radiographic progression per RECIST 1.1 as determined by the investigator or the date of the decision to permanently discontinue study treatment. (Please see Appendix B for the Open-Label Phase, Child-Pugh assessments will be discontinued for the Maintenance Phase).

Blood samples for pharmacogenetic, plasma biomarker, serum bone marker analyses, and potential CTC analysis (Section 5.7.11) will be collected according to the schedule in Appendix A. (These assessments will be discontinued for the Open-Label Phase or Maintenance Phase.)

In addition, tumor tissue (archival or recently biopsied) will be obtained (Section 5.7.11) at enrollment whenever available for exploratory analysis of MET and potentially other pathway components or modulators associated with the mechanism of action of cabozantinib as predictive biomarkers.

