### **5.5.2 Extended Follow-up**

Following treatment discontinuation for whatever reason, subjects will continue to be followed either via clinic visit or telephone contact approximately every 8 weeks for the following information unless the subject withdraws consent from all aspects of the study:

- Survival status of subject or date of death and primary cause of death

- Receipt of subsequent anticancer therapies (drug or procedure name and dates)

Radiographic disease assessments, EQ-5D-5L, and Child-Pugh assessments are to continue in the Extended Follow-Up period as necessary per the schedule for these assessments in Appendix A.

Subjects will be followed until death or until the Sponsor's decision to no longer collect these data.

At each contact, the investigator (or designee) will determine if the subject died, and if so, record the date and cause of death. All efforts must be undertaken by the study sites to determine the date of death (or date subject last known alive at the time of a data cut-off). This may include, but not necessarily be limited to telephone contacts, communication at study visits, registered letters, and reviews of local obituaries and government death records. If subject is lost to follow-up, multiple attempts to contact must be made and documented in the subject records.

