#### **6.1.2 Subsequent Dose Administration**

Subjects should fast (with the exception of water) for at least 2 hours after eating the evening meal before taking their dose of study drug. After the 2-hour fast and before going to bed, subjects are to take the tablets with a minimum of 8 oz (240 mL) water with no more food intake for at least 1 hour postdose. If the subject's schedule requires taking cabozantinib during the day, the subject should be instructed to follow the same fasting recommendations.

Subjects should be instructed to not make up vomited doses or missed doses and to maintain the planned dosing schedule. Subjects should not make up for missed doses if more than 12 hours

have elapsed after the time the subject would usually take study drug. In the event of missed doses, subjects should not take two doses to make up for the one the subject missed.

Dose reductions and interruptions due to tolerance issues are outlined in Section 6.5.1.

Subjects will receive blinded study drug as long as they continue to experience clinical benefit in the opinion of the investigator or until the earlier of unacceptable toxicity, the need for subsequent systemic anticancer therapy/liver-directed local anticancer therapy, or until any of the other reasons for treatment discontinuation described in Section 3.6.

Treatment may continue after disease progression per RECIST 1.1 has been determined by the investigator as long as the investigator believes that the subject is still receiving clinical benefit from study treatment and that the potential benefit of continuing study treatment outweighs potential risk.

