**Table 1: Protocol Version History** 

Date	Version	Primary Reason(s) for Amendment
12 March 2013	Original Protocol	Not Applicable
23 April 2014	Amendment 1.0	Provides additional clarification to 3 inclusion criteria and 4 exclusion criteria.
		Additional Child-Pugh testing time-points have been added.
		Specifies that all subjects will have hepatitis virus testing via central laboratory prior to enrollment but those results will not be required for randomization.
		Introduces the Maintenance Phase, which subjects will enter when sufficient data have been collected to evaluate all study endpoints.

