## 7.5 Exploratory Efficacy Endpoints

Each exploratory endpoint will be analyzed using an appropriate two-sided statistical test without adjustment for multiplicity unless specified otherwise. Statistical results for exploratory endpoints will be considered descriptive. Exploratory analyses will be performed using all subjects in the ITT population unless specified otherwise.

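### The SAP's only post-baseline Child-Pugh summary stops at end of treatment, so scores the protocol collects off drug in the blinded phase have no planned summary

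*SAP*

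**What the plan says.** SAP 7.5.6 consists of a single sentence: "Change from baseline in Child-Pugh categories will be summarized as a shift table at each time point through to end of treatment". It does not say what date marks the end of treatment. It sits in SAP 7.5, where "Exploratory analyses will be performed using all subjects in the ITT population unless specified otherwise" and where results are treated as descriptive.

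Protocol 5.2 collects for longer: "Child-Pugh assessments should continue regardless of whether study treatment is given, reduced, interrupted, or discontinued until the later of 8 weeks after radiographic progression" or the decision to stop study drug permanently, whichever falls later. Appendix A gives the same rule with an 8-week interval, and Protocol 3.3 repeats the stopping point. Protocol 5.5.2 carries collection past treatment: "Radiographic disease assessments, EQ-5D-5L, and Child-Pugh assessments are to continue in the Extended Follow-Up period as necessary per the schedule" in Appendix A.

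The version history in the SAP (Table 1) records, for Amendment 1.0, that "Additional Child-Pugh testing time-points have been added".

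**The concern.** The analysis window is shorter than the collection window, and the SAP gives no reason. Leaving the table is also linked to what the table measures. Protocol 6.7.3 lists irreversible hepatic dysfunction and suspected drug-induced liver injury among the reasons to end study drug. A subject who stops for either reason drops out of the Child-Pugh table because the liver has worsened, while scores go on being collected.

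Visits are 8 weeks apart, so the score closest to such a stop may itself be excluded. A subject who stops at week 12 has an on-treatment score at week 8, and the next one, at week 16, falls outside the table. From then on, each column conditions on still taking drug, which is a post-randomization event, in a section whose default population is ITT.

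At stake is how completely the report describes liver function in a population enrolled as Child-Pugh A. Laboratory tables do not fully replace the score, because it also grades ascites and encephalopathy (Protocol 5.7.12 and Appendix E).

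**Working it through.** There is no power, alpha or sample-size figure to reproduce here. The check compares the two windows and then illustrates the scale.

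**1. The windows side by side**
- Analysis (SAP 7.5.6): each time point up to end of treatment.
- Collection, blinded phase (Protocol 5.2, 5.5.2, Appendix A): every 8 weeks until max(progression + 8 weeks, discontinuation decision).
- Difference: scores after the stop and up to progression + 8 weeks, for subjects who stop before that date.
- A search of the SAP finds no other post-baseline Child-Pugh summary.

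**2. Where the difference is nil or unclear**
- Treatment past progression is permitted (Protocol 6.1.2: "Treatment may continue after disease progression per RECIST 1.1 has been determined by the investigator as long as the investigator believes" there is benefit). A subject treated more than 8 weeks past progression has no off-drug Child-Pugh requirement.
- In the Open-Label Phase, collection ends with the discontinuation decision (Appendix B schedule). In the Maintenance Phase there is none (Protocol 5.2).
- For subjects never dosed, Protocol 5.2 says "HRQOL, and radiographic tumor assessments, as well as survival follow-up, are to be performed per protocol even for subjects randomized but who never receive" treatment. Child-Pugh is not named in that sentence. These subjects also have no end of treatment, so SAP 7.5.6 does not place them although they are in the ITT population.

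**3. A comparable measure in the same SAP**
AFP follows the same collection rule (Protocol 5.7.7). SAP 7.5.4 summarizes it at each scheduled post-baseline visit and gives best and worst change from all available data. SAP 7.5.6 has neither feature.

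**4. Loss for one subject**
Assume the score at the stopping visit counts as on treatment and the subject is alive and assessed at every later scheduled visit.
- Progression and stop at week 8: scores at weeks 8 and 16, so 1 of 2 is unused.
- Both at week 16: scores at weeks 8, 16 and 24, so 1 of 3.
- Both at week 24: 1 of 4.
- Stop at week 8 without progression, progression at week 24: scores at weeks 8, 16, 24 and 32, so 3 of 4.

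**5. How fast the on-treatment table thins**
Inputs: average time on treatment m = 3 to 5 months (Protocol 3.2, not split by arm); design median survival 8.2 months on placebo and 10.8 on cabozantinib (Protocol 9.9); a month of 30.4375 days (SAP 4). Assumption: time on treatment is exponential. With t = weeks × 7 / 30.4375, the share on treatment is exp(−t/m) and the share alive is 0.5^(t/median).

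| Week | t (months) | On treatment, m = 3 to 5 | Alive, placebo / cabozantinib |
|---|---|---|---|
| 8 | 1.84 | 54% to 69% | 86% / 89% |
| 16 | 3.68 | 29% to 48% | 73% / 79% |
| 24 | 5.52 | 16% to 33% | 63% / 70% |
| 32 | 7.36 | 9% to 23% | 54% / 62% |

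The gap between the last two columns is not the recoverable amount. Only subjects who are off drug and not yet 8 weeks past progression are still scored, and the documents do not give their number.

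**6. Can a direction between arms be derived?**
No. Faster progression makes the single post-progression score a larger share of the total (1 of 2 against 1 of 4 in step 4), which would cost the placebo arm more. More frequent stops before progression (the 3 of 4 case) would cost the cabozantinib arm more. An illustrative simulation used assumed PFS medians of 5.2 and 2.0 months, 30% treated on average 6 weeks past progression, and median survival of 6 months from the earlier of stop or progression. With toxicity stops assumed more frequent on cabozantinib, 61.4% of scheduled scores fell on treatment in that arm against 67.9% on placebo. With one toxicity-stop mean of 12 months in both arms, the order reversed: 61.5% against 59.1%. The sign follows the assumed stopping rates, which the documents do not supply.

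**The case against.** The strongest reply is that little depends on this table. It carries no test, and Child-Pugh change is not among the endpoints listed in Protocol 2.2 or SAP 2.3. Hepatic adverse events that lead to discontinuation are tabulated (SAP 8.1). Adverse events and laboratory results run to 30 days after the discontinuation decision (SAP 4.5, 8.1, 8.3.2), including graded bilirubin and albumin, liver-function shifts and Hy's Law screening. Deaths are summarized both within and beyond 30 days of last dose (SAP 8.2). All of this stands. A reader might infer that liver deterioration after stopping goes unreported, and the documents do not support that. What has no summary is the Child-Pugh category itself once drug is stopped.

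It is also fair to say that an on-treatment table answers a legitimate tolerability question, that scores recorded up to the stop are kept, and that the all-collected table would include scores taken after subsequent anticancer therapy. These are reasons to keep the on-treatment display next to a fuller one. They do not explain why required assessments should have no summary.

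Finally, using every collected score does not remove selection, because collection itself ends at a time that depends on progression and discontinuation. That is correct, and the change should be described as reducing selection.

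**Conclusion.** The point holds as a mismatch between what is collected and what is summarized. It applies to blinded-phase subjects who stop drug before 8 weeks past progression. It affects one exploratory, descriptive summary. OS, PFS, ORR and type I error are untouched. It is worth correcting because the correction is cheap and the reason for leaving the table can be the outcome itself.

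Three stronger readings are tempting and should not be drawn:
- That off-drug scores exist for every randomized subject. The exceptions in step 2 rule this out.
- That the arms are compared over unequal time. No arm-specific treatment duration or stopping rate is given, and the direction turns on assumptions (step 6).
- That shifts to B or C are biased toward no change. Neither the documents nor the check above models Child-Pugh category, so neither direction nor size of bias is established.

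The figures in step 5 rest on the exponential assumption and a pooled average. They show the scale of thinning and do not estimate lost data. The amendment entry shows only that the schedule was extended. The previous schedule is not available, so it supports stating the denominator and nothing more.

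**What to change.** Amend SAP 7.5.6 so that:
- shift tables in the ITT population use all Child-Pugh assessments collected after randomization, on or off study treatment, with the number assessed at each time point as denominator and the number alive shown beside it;
- worst post-baseline category is added, as a shift from baseline;
- the on-treatment shift table stays as a separate display, with the date that ends treatment defined;
- scores after crossover in an Open-Label Phase stay out of both arms, as Protocol 9.10 already requires.

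Cost: a change of wording and one or two extra tables, with no new data collection. Two limits should be footnoted: some scores will follow subsequent anticancer therapy, and some selection remains because collection ends at the later of 8 weeks past progression or discontinuation.

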# 7.5.7 Health Care Resource Utilization

For this study the following health care resource utilization (HCRU) parameters collected during the study observation period will be summarized:

- Days of hospitalization due to SAEs
- Days in intensive care unit (ICU) due to SAEs
- Number of emergency room (ER) visits due to SAEs
- Number of surgeries

The summaries will include:

- Number and percentage of subjects in each category of HCRU
- Descriptive statistics for each HCR category amongst those subjects who utilized the respective resource
- Total number of days or visits as applicable for each HCRU
- Per person year summary for each HCRU

To calculate the per person year value for a subject for a HCRU parameter, the numerator is the sum of the days or visits for that subject for the parameter; and the denominator is defined as: (safety observation period – date of randomization + 1) / 365.25.

# 7.5.8 Pharmacokinetics (PK)

Pharmacokinetics analyses are outside the scope of this plan. A separate PK analysis plan and report will be provided.

# 7.6 Subgroups

The following subgroups based on baseline characteristics and stratification factors will be explored for primary and secondary efficacy endpoints

- Age category
  - o <65 years
  - $\circ$  65 to <75 years
  - o 75 to <85 years
  - $\circ$   $\geq$ 85 years
- o Sex

- Male
- Female
- o Race
  - Asian
  - Black or African American
  - White
  - Rest of the races reported/Not Reported
- o Geographic Regions 1
  - Asia (excluding Japan)
  - Europe/Australia/New Zealand
  - North America (Canada/USA)
  - Other
- o Geographic Regions 2
  - Asia
  - Other Region
- o ECOG Performance status at baseline:
  - **-** (
  - 1
  - Missing
- Etiology of disease per stratification factors per IxRS:
  - HBV [with or without HCV]
  - HCV [without HBV]
  - Other
- o Current etiology of disease (per cancer history CRF):
  - HBV [without HCV] (Yes/No/Unk)
  - HCV [without HBV] (Yes/No/Unk)
  - HBV and HCV (Yes/No/Unk)
  - Alcoholism (Yes/No/Unk)
  - Nonalcoholic Steatohepatitis (NASH) (Yes/No/Unk)
  - Other (Yes/No/Unk)
- o Presence of extrahepatic spread of disease and/or macrovascular invasion (per IxRS):
  - Yes
  - No
- Presence of extrahepatic spread of disease and/or macrovascular invasion (per cancer history CRF):
  - Yes

- No
- Visceral sites other than liver, bone, bone+visceral sites other than liver per tumor assessment CRFs per investigator. Visceral sites other than liver will include lung kidney, pancreas and other sites based upon a manual review of the reported sites after all data has been entered in the database
- o Prior systemic non-radiation anti-cancer therapy regimens for advanced HCC per subject per history of non-radiation anti-cancer therapy CRF (1 vs  $\geq$  2)
- Prior receipt of PD-1/PD-L1 per history of non-radiation anti-cancer therapy CRF (Yes, No)
- Prior receipt of Regorafenib per history of non-radiation anti-cancer therapy CRF (Yes, No)
- Prior receipt of Lenvatinib per history of non-radiation anti-cancer therapy CRF (Yes, No)
- Prior receipt of Tivantinib per history of non-radiation anti-cancer therapy CRF (Yes. No)
- Prior receipt of Ramucirumab per history of non-radiation anti-cancer therapy CRF (Yes. No)
- o VEGF-A amplification in circulating tumor cells (Yes, No, Unknown)
- AFP (<400 ng/mL,  $\ge 400 \text{ ng/L}$ ) at baseline
- o Tumor MET status
  - High
  - Low or Negative
  - Unknown

# 8 SAFETY SUMMARIES

All safety analyses will be performed using all subjects in the Safety population. No formal statistical comparison between the two treatments arms is planned.

Safety and tolerability will be assessed by the incidence of treatment emergent-adverse events (TEAEs), changes in laboratory parameters and vital signs from baseline, and ECOG PS.

An Independent Data Monitoring Committee (IDMC) will monitor safety during the study on a regular basis. The committee will operate independently from the Sponsor and the clinical investigators.

The primary responsibility of the IDMC is to review the accumulating safety data on a regular and an ad hoc basis and make recommendations to the Sponsor regarding the continued conduct of the study. Safety data will be provided at regular intervals to the IDMC in the form of summary reports or data listings from the Sponsor (blinded) or its designated representative (unblinded).

Details regarding IDMC membership, schedule and format of meetings, format for presentation of data, access to interim data, method and timing of providing interim reports to the IDMC, and other issues relevant to committee operations are described in the IDMC charter

The IDMC members will use their expertise, experience, and judgment to evaluate the safety data from the trial and to recommend to the Sponsor whether the trial should continue or be stopped early for safety. No formal statistical rules recommending early stopping for safety are planned.

